**PROTOCOL VERSION HISTORY**

Version 6 dated December 6, 2019  
Version 5 dated August 8, 2019  
Version 4 dated May 29, 2018  
Version 3 dated September 1, 2017  
Version 2 dated August 1, 2017  
Version 1.2 dated January 25, 2017  
Version 1.1 dated December 2, 2016  
Version 1 dated October 28, 2016

## **DEFINITIONS OF TERMS USED**

AE	adverse event
AIDS	acquired immunodeficiency syndrome
ALT	alanine transaminase
AST	aspartate transaminase
BMS	Bristol Myers Squibb
BP	blood pressure
BUN	blood urea nitrogen
CBCD	complete blood count with differential
CR	complete response
CrCl	creatinine clearance
CT	computed tomography
DILI	drug induced liver injury
DSMC	Data Safety Monitoring Committee
ECOG	Eastern Cooperative Oncology Group
eCRF	electronic case report form
FDA	Food and Drug Administration
FSH	follicle stimulating hormone
GCP	Good Clinical Practice
HBV	hepatitis B virus
HCC	Hollings Cancer Center
HCG	human chorionic gonadotropin
HCV	hepatitis C virus
HIV	human immunodeficiency virus
HNSCC	head and neck squamous cell carcinoma
HR	heart rate
IB	Investigator's Brochure
ICH	International Council of Harmonisation
IIT	Investigator Initiated Trial
IRB	Institutional Review Board
IV	intravenous
LFT	liver function test
MRI	magnetic resonance imaging
MUSC	Medical University of South Carolina
NCI CTCAE	National Cancer Institute Common Terminology for Adverse Events
OCSCC	oral cavity squamous cell carcinoma
pCR	pathologic complete response
PET	positron emission tomography
PR	partial response
RECIST	response evaluation criteria in solid tumors
SAE	serious adverse event
SIS Unit	Sponsor-Investigator Support Unit
SOP	standard operating procedure
ULN	upper limit of normal
WBC	white blood cell
WOCBP	woman of child bearing potential

## 1 SCHEMA

## **2 OBJECTIVES**

### **2.1 PRIMARY OBJECTIVE**

To determine the pathological overall response rate (PR+CR) of neoadjuvant pre- surgical PD-1 inhibition in patients with surgically amenable oral cavity cancer.

### **2.2 SECONDARY OBJECTIVES**

- To evaluate the systemic and intratumoral immune activation following PD-1 blockade.
- To determine immune reactivity to autologous OCSCC.

### **2.3 EXPLORATORY OBJECTIVES**

- To compare genomic sequencing of patients before and after therapy with Nivolumab.

## **3 BACKGROUND**

### **3.1 CLINICAL BURDEN OF HNSCC**

Over 300,000 patients develop squamous cell carcinoma of the oral cavity (OCSCC) worldwide and nearly half of these patients die from the disease each year [1]. The development of regional metastases in oral cavity cancer decreases the 5-yr survival by 50%, and therefore advanced OCSCC portends a poor prognosis with estimated survival rates at 5 years ranging from 35-45% [2, 3]. Treatment of advanced oral cavity cancer often requires complex, multimodality therapy, employing surgical resection followed by post-operative radiation, with the addition of cisplatin-based chemotherapy for patients with high-risk of failure [4]. Despite these comprehensive treatment strategies, OCSCC recurs in 25-48% of patients [3, 5, 6]. Additionally, advances in reconstructive procedures have improved post-operative function of oral cavity cancer patients but these surgeries continue to be associated with significant morbidity including disfigurement, speech and swallowing deficits, and tracheostomy or gastrostomy tube dependence. Given the poor prognosis, high recurrence rates, and associated post-operative morbidities observed in OCSCC, it is evident new strategies are needed to treat and aid in the management of OCSCC [7, 8].

### **3.2 BENEFITS OF NEOADJUVANT TREATMENT**

Neoadjuvant therapy is now being applied in multiple cancer types and has provided a new paradigm in the treatment of patients with breast and esophageal cancer in terms of overall and disease-free survival [9-12]. In the case of unresectable HNSCC, neoadjuvant chemotherapy has been applied prior to definitive radiotherapy or chemoradiotherapy with significant response rate in several phase II and III studies [13-15]. The results from these clinical trials support the concept that neoadjuvant treatment can be considered as a novel therapeutic strategy for the treatment of advanced HNSCC. Neoadjuvant chemotherapy prior to definitive surgery has been explored for the treatment of HNSCC with high rates of initial response ranging from 30-40% but a recent meta-analysis of 28 randomized trials revealed a modest survival benefit of only 6%[16-18]. Neoadjuvant treatment prior to definitive

surgery has been shown to determine clinical efficacy and define molecular biomarkers predictive of response and has been tested in several studies including one at our own institution investigating the mTOR inhibitor, Rapamycin [16, 19-21]. In general, the potential benefits of effective neoadjuvant therapies include 1) the assessment of clinical response to novel, mechanism-based treatment options which can decrease tumor burden and thus reduce the extent of surgery [17]; 2) the exploration of molecular changes in cancer cells and surrogate tissues, such as blood, may provide valuable biomarkers to identify patients that may benefit the most from new targeted therapies [22]. A clinical response to neoadjuvant chemotherapy has prognostic value in multiple cancers, as pathologic complete response at the time of surgery is a recognized and validated surrogate marker for good clinical outcome [23, 24].

### **3.3 IMMUNOTHERAPY IN HNSCC**

Because of the combination for the need of new therapies and the benefits of a neoadjuvant treatment strategy, the possibility of immunotherapeutic approaches for HNSCC patients has gained interest. Unfortunately, HNSCC patients have profound immune defects that are associated with a worse outcome and have been attributed to tumor production of inhibitory mediators and tumor-induced immune inhibitory cell populations [25-30]. Programmed Death receptor I (PD-1) and its ligand (PD-L1) appear to contribute to this immune dysfunction as 50-60% lymphocytes from HNSCC patients have upregulated PD-1 expression and PD-1 blockade enabled lymphocyte proliferative reactivity to stimulation and indirectly overcame immune unresponsiveness by modulating immune inhibitory populations, including T regulatory cells [30-33]. Furthermore, tumor PD-L1 expression has been associated with improved objective response and clinical benefit in multiple tumor types [34]. Since 60-80% of OCSCC express PD-L1, it is anticipated PD-1 blockade will benefit 20-25% of patients with OCSCC [30, 33, 34]. Most recently the Checkmate 141 Phase III trial revealed in patients with treatment-resistant and rapidly progressive head and neck carcinoma that nivolumab treatment was associated with an improved 12-month overall survival of 36%, compared with 17% in the Investigator Choice arm [40, 41].

### **3.4 STUDY RATIONALE**

Our past clinical trials with HNSCC patients have shown the feasibility of pre-surgical targeted or immunotherapy followed by multi-modality treatments combining surgery and adjuvant therapy leading to an improvement in recurrence free survival [35-37]. A similar multi-modality treatment is being proposed in this application to overcome immune lethargy by Nivolumab treatment to block PD 1 between the time of OCSCC diagnosis and surgical treatment. This duration of time will allow for the administration of three doses of Nivolumab given on Days 1, 15 and 29. The primary objective of the proposed study is to determine the efficacy of neoadjuvant PD-1 inhibition in patients with oral cavity cancer undergoing definitive surgical resection. In addition to assessing the clinical efficacy of Nivolumab, secondary objectives will be to analyze the effectiveness of PD-1 antibodies at

restoring the immune reactivity in the peripheral blood as well as stimulating intratumoral immune activity. The rationale for this approach is based on the overexpression of lymphoid PD 1 in the HNSCC environment along with our prior demonstration of the feasibility of pre-surgical immune modulatory treatment or targeted mTOR therapy having positive post-surgical clinical effectiveness [30, 35, 36, 38]. Additionally, blocking PD 1 prior to surgical excision will allow restoration of immune competence to not only enable pre surgical immune responsiveness to HNSCC, but also post-surgical immunological surveillance for residual cancer.

We hypothesize 25-30% overall response rate (PR+CR) in patients with OSCC, and these patients will reveal a systemic and intratumoral response following anti-PD-1 therapy along with immune reactivity to autologous OCSCC.

## **4 SUBJECT SELECTION**

### **4.1 INCLUSION CRITERIA**

Patients eligible for study participation must meet all of the following criteria

1. Newly diagnosed histologically proven locoregional OCSCC without evidence of distant metastases and a clinically determined T-stage of 2-4 (based on AJCC Staging Manual v.7 guidelines),

#### **OR**

Recurrent or persistent histologically proven locoregional OCSCC that was initially treated with surgery alone, and a clinically determined recurrent T-stage of 2-4 (based on AJCC Staging Manual v.7 guidelines).

**Note** – OCSCC includes the subsites of oral tongue, floor of mouth, gingiva, retromolar trigone, and buccal mucosa.

**Note** – To allow sufficient tumor tissue for the immunological analyses, patients with T-stage 1 OCSCC will be excluded

2. Greater than or equal to 18 years of age
3. ECOG performance status of 0 or 1
4. Screening labs must meet the following criteria and must be obtained within 14 days prior to registration:
  - WBC  $\geq 2,000/\mu\text{L}$
  - Absolute Neutrophil Count  $\geq 1,500/\mu\text{L}$
  - Platelets  $\geq 100 \times 10^3/\mu\text{L}$
  - Hemoglobin  $\geq 9.0 \text{ g/dL}$

- Serum creatinine  $\leq 1.5 \times \text{ULN}$  or  $\text{CrCl} \geq 40 \text{ mL/min}$  (if using the Cockcroft-Gault formula below):

$$\text{Female CrCl} = \frac{(140 - \text{age in years}) \times \text{weight in kg} \times 0.85}{72 \times \text{serum creatinine in mg/dL}}$$

$$\text{Male CrCl} = \frac{(140 - \text{age in years}) \times \text{weight in kg} \times 1.00}{72 \times \text{serum creatinine in mg/dL}}$$

- AST/ALT  $\leq 3 \times \text{ULN}$
- Total Bilirubin  $\leq 1.5 \times \text{ULN}$  (except subjects with Gilbert Syndrome, who can have total bilirubin  $< 3.0 \text{ mg/dL}$ )

5. Reproductive Status:

WOCBP must use appropriate method(s) of contraception. WOCBP should use an adequate method to avoid pregnancy for 23 weeks (30 days plus the time required for nivolumab to undergo five half-lives) after the last dose of investigational drug.

Men receiving nivolumab and who are sexually active with WOCBP will be instructed to adhere to contraception with a failure rate of less than 1% per year for a period of 31 weeks after the last dose of investigational product.

WOCBP is defined as any female who has experienced menarche and who has not undergone surgical sterilization (hysterectomy or bilateral oophorectomy) or who is not postmenopausal. Menopause is defined clinically as 12 consecutive months of amenorrhea in a woman over 45.

Women of childbearing potential must have a negative serum pregnancy test (minimum sensitivity 25 IU/L or equivalent units of HCG) within 24 hours prior to registration

Women who are not of childbearing potential (i.e., who are postmenopausal or surgically sterile) and azoospermic men, are not required to use contraception.

See [appendix A](#) for acceptable methods of contraception.

## 4.2 EXCLUSION CRITERIA

Patients eligible for study participation CANNOT meet any of the following criteria

1. Prior immunotherapy or treatment with another anti PD 1 agent
2. Prior chemotherapy including Cetuximab or radiation therapy
3. Previous severe hypersensitivity reaction to another monoclonal antibody
4. Women who are pregnant, lactating or expecting to conceive
5. Men who are expecting to father children within the research period
6. Known history of HIV or AIDS
7. Positive test for HBV sAg or HCV antibody indicating acute or chronic infection

8. Concomitant malignancies except cutaneous squamous cell carcinoma or basal cell carcinoma
9. Unresectable primary tumor or regional disease; presence of distant metastases.
10. History of pneumonitis or interstitial lung disease
11. Active, known or suspected autoimmune disease. Note: Subjects are permitted to enroll if they have vitiligo, type I diabetes mellitus, residual hypothyroidism due to autoimmune condition only requiring hormone replacement, psoriasis not requiring systemic treatment, or conditions not expected to recur in the absence of an external trigger
12. Presence of condition requiring systemic treatment with either corticosteroids (> 10 mg daily prednisone or equivalents) or other immunosuppressive medications within 14 days of study drug administration. Inhaled or topical steroids and adrenal replacement doses > 10 mg daily prednisone equivalents are permitted in the absence of active autoimmune disease

#### **4.3 INCLUSION OF WOMEN AND MINORITIES**

Both men and women of all races and ethnic groups are eligible for this trial.

#### **4.4 SUBJECT REGISTRATION**

The SIS Unit will provide subject registration services for the study. After obtaining signed informed consent and completion of required baseline assessments, eligible subjects will be registered. All study subjects will undergo an eligibility audit prior to registration. A unique subject number will be assigned to each patient. A registration confirmation will be emailed to the enrolling study team at the time of registration. This confirmation will include the subject's assigned cohort dose level and study ID number. Registrations may occur between 8AM and 5PM EST, Monday through Friday. Registrations may take place outside of this timeframe if prior arrangements are made.

### **5 STUDY INTERVENTION**

#### **5.1 NIVOLUMAB ADMINISTRATION**

Nivolumab will be given every two weeks at a dose of 3mg/kg will be administered as a 60 minute IV infusion (+/- 10 minutes). Study drug will be administered on an outpatient basis. Subjects may be dosed no less than 12 days from the previous dose of drug.

REGIMEN DESCRIPTION			
Agent	Dose	Route	Schedule
Nivolumab	3mg/kg	IV	Cycle 1 = Day 1 Cycle 2 = Day 15 Cycle 3 = Day 29  Response assessment

		Cycle 4 = Day 43 if stable disease or response after day 29.
--	--	--

The dosing calculations should be based on the actual body weight at baseline. If the subject's weight on the day of dosing differs by > 10% from the weight used to calculate the original dose, the dose must be recalculated. All doses should be rounded to the nearest milligram. **There will be no dose reductions allowed.**

Nivolumab injection is to be administered as an IV infusion through a 0.2-micron to 1.2-micron pore size, low-protein binding polyethersulfone membrane in-line filter at the protocol-specified doses. It is not to be administered as an IV push or bolus injection. Nivolumab injection can be infused undiluted (10 mg/mL) or diluted with 0.9% Sodium Chloride Injection, USP or 5% Dextrose Injection (USP to protein concentrations as low as 1 mg/mL). Care must be taken to assure sterility of the prepared solution as the product does not contain any antimicrobial preservative or bacteriostatic agent.

Subjects should be carefully monitored for infusion reactions during nivolumab administration. If an acute infusion reaction is noted, subjects should be managed according to Protocol Section 5.3.

## 5.2 SURGICAL RESECTION

Between days 28-35, subjects will be evaluated for disease progression through clinical and radiographic tumor assessment, and for toxicity by history, physical and clinical labs. In the event of disease progression, subjects will proceed to definitive surgical resection between days 36-42 and no later than 50 days after randomization. If disease is stable or response is observed, subjects will have the fourth administration of nivolumab on Day 43 (+/- 1 day) followed by definitive surgical resection on day 50-56 and no later than 60 days randomization.

## 5.3 PRE AND POST MEDICATIONS

Since nivolumab contains only human immunoglobulin protein sequences, it is unlikely to be immunogenic and induce infusion or hypersensitivity reactions. However, if such a reaction were to occur, it might manifest with fever, chills, rigors, headache, rash, pruritis, arthralgias, hypo- or hypertension, bronchospasm, or other symptoms of allergic-like reactions.

All Grade 3 or 4 infusion reactions should be reported as an SAE if criteria are met. Infusion reactions should be graded according to NCI CTCAE v. 4.0 guidelines.

Treatment recommendations are provided below and may be modified based on local treatment standards and guidelines as appropriate:

- **For Grade 1 symptoms:** (Mild reaction; infusion interruption not indicated; intervention not indicated)

Monitor subject until recovery from symptoms. The following prophylactic premedications are recommended for future infusions: diphenhydramine 50 mg (or equivalent) and/or paracetamol 325 to 1000 mg (acetaminophen) at least 30 minutes before additional nivolumab administrations.

- **For Grade 2 symptoms:** (Moderate reaction requires therapy or infusion interruption but responds promptly to symptomatic treatment [eg, antihistamines, non-steroidal anti inflammatory drugs, narcotics, corticosteroids, bronchodilators, IV fluids]; prophylactic medications indicated for 24 hours).

Stop the nivolumab infusion, begin an IV infusion of normal saline, and treat the subject with diphenhydramine 50 mg IV (or equivalent) and/or paracetamol 325 to 1000 mg (acetaminophen); remain at bedside and monitor subject until resolution of symptoms. Corticosteroid or bronchodilator therapy may also be administered as appropriate. If the infusion is interrupted, then restart the infusion at 50% of the original infusion rate when symptoms resolve; if no further complications ensue after 30 minutes, the rate may be increased to 100% of the original infusion rate. Monitor subject closely. If symptoms recur then no further nivolumab will be administered at that visit. Administer diphenhydramine 50 mg IV, and remain at bedside and monitor the subject until resolution of symptoms. The amount of study drug infused must be recorded on the eCRF. The following prophylactic premedications are recommended for future infusions: diphenhydramine 50 mg (or equivalent) and/or paracetamol 325 to 1000 mg (acetaminophen) should be administered at least 30 minutes before additional nivolumab administrations. If necessary, corticosteroids (recommended dose: up to 25 mg of IV hydrocortisone or equivalent) may be used.

- **For Grade 3 or Grade 4 symptoms:** (Severe reaction, Grade 3: prolonged [ie, not rapidly responsive to symptomatic medication and/or brief interruption of infusion]; recurrence of symptoms following initial improvement; hospitalization indicated for other clinical sequelae [eg, renal impairment, pulmonary infiltrates]). Grade 4: (life threatening; pressor or ventilatory support indicated).

Immediately discontinue infusion of nivolumab. Begin an IV infusion of normal saline, and treat the subject as follows. Recommend bronchodilators, epinephrine 0.2 to 1 mg of a 1:1,000 solution for subcutaneous administration or 0.1 to 0.25 mg of a 1:10,000 solution injected slowly for IV administration, and/or diphenhydramine 50 mg IV with methylprednisolone 100 mg IV (or equivalent), as needed. Subject should be monitored until the investigator is comfortable that the symptoms will not recur. Nivolumab will be permanently discontinued. Investigators should follow their institutional guidelines for the treatment of anaphylaxis. Remain at bedside and monitor subject until recovery from symptoms.

In the case of late-occurring hypersensitivity symptoms (eg, appearance of a localized or generalized pruritus within 1 week after treatment), symptomatic treatment may be given (eg, oral antihistamine, or corticosteroids).

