## **6 DOSE MODIFICATIONS**

Dose reductions or dose escalations are not permitted. Dose delays due to adverse events are not permitted. If an AE occurs causing a missed dose, the subject will stop the nivolumab administration schedule and proceed to surgery. Dose delays for other reasons are allowed with prior approval from the Sponsor-Investigator.

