### **6.2 DISCONTINUATION CRITERIA**

Subjects may discontinue study treatment at any time. Subjects may be removed from study for any of the following reasons:

- Radiographic disease progression that is not amendable to resection
- Clinical disease progression that would not benefit from surgery
- Inter-current illness that would, in the judgment of the investigator, affect assessments of clinical status to a significant degree or require discontinuation of study drugs
- Completion of protocol treatment.
- Death
- Subject non-compliance
- Treatment should be permanently discontinued for the following:
  - Any Grade 2 drug-related uveitis or eye pain or blurred vision that does not respond to topical therapy and does not improve to Grade 1 severity within the re-treatment period OR requires systemic treatment
  - Any Grade 3 non-skin, drug-related adverse event lasting > 7 days, with the following exceptions for drug-related laboratory abnormalities, uveitis, pneumonitis, bronchospasm, hypersensitivity reactions, infusion reactions, and endocrinopathies:
    - Grade 3 drug-related uveitis, pneumonitis, bronchospasm, hypersensitivity reaction, or infusion reaction of any duration requires discontinuation
    - Grade 3 drug-related endocrinopathies adequately controlled with only physiologic hormone replacement **do not** require discontinuation

- Grade 3 drug-related laboratory abnormalities **do not** require treatment discontinuation except those noted below
  - Grade 3 drug-related thrombocytopenia > 7 days or associated with bleeding requires discontinuation
  - Any drug-related LFT abnormality that meets the following criteria require discontinuation:
    - AST or ALT > 8 x ULN
    - Total bilirubin > 5 x ULN
    - Concurrent AST or ALT > 3 x ULN and total bilirubin > 2 x ULN
- Any Grade 4 drug-related adverse event or laboratory abnormality, except for the following events which **do not** require discontinuation:
  - Isolated Grade 4 amylase or lipase abnormalities that are not associated with symptoms or clinical manifestations of pancreatitis and decrease to < Grade 4 within 1 week of onset.
  - Isolated Grade 4 electrolyte imbalances/abnormalities that are not associated with clinical sequelae and are corrected with supplementation/appropriate management within 72 hours of their onset
  - Grade 4 lymphopenia or leukopenia

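### Section 5.3's Grade 2 infusion-reaction steps can lead to re-dosing a patient whose symptoms recur after restart, although the next bullet makes recurrence Grade 3 and stops the drug permanently

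*Combined protocol and SAP*

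**What the plan says.** Section 5.3 manages infusion reactions by grade. For Grade 2, the infusion is stopped and the patient treated. If it was interrupted, staff are told: "then restart the infusion at 50% of the original infusion rate when symptoms resolve". For symptoms that return after that, the instruction is: "If symptoms recur then no further nivolumab will be administered at that visit". Intravenous diphenhydramine and bedside observation follow. The paragraph then turns to later doses: "The following prophylactic premedications are recommended for future infusions". That sentence makes no exception for a patient whose symptoms recurred.

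The next bullet covers Grades 3 and 4. Its description of Grade 3 includes "recurrence of symptoms following initial improvement", and its instruction on dosing is "Nivolumab will be permanently discontinued".

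Section 6.2 lists what ends treatment permanently. For Grade 3 drug-related events of this kind it reads: "hypersensitivity reaction, or infusion reaction of any duration requires discontinuation".

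Section 6 adds a general rule: "If an AE occurs causing a missed dose, the subject will stop the nivolumab administration schedule and proceed to surgery". It does not say whether a partly infused dose is a missed one.

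**The concern.** A clinician treating a Grade 2 reaction is already inside the Grade 2 steps when symptoms return. Those steps say what to do that day and then look ahead to premedicated infusions. Nothing tells the clinician to regrade the event or move to the next bullet. Yet the same event, on the wording of that bullet, is Grade 3 and ends dosing.

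What is at stake is patient safety: a second exposure after a reaction that has already recurred on restart. Immediate care differs too. The Grade 2 recurrence step gives an antihistamine, whereas the Grade 3 bullet recommends bronchodilators, epinephrine and/or an antihistamine with methylprednisolone, as needed.

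**Working it through.** The check is mainly a comparison of texts.

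1. *Sequence under the Grade 2 paragraph.* Reaction, stop, symptoms resolve, restart at half rate, symptoms return. Because restart waits for resolution, improvement has come before the return.
2. *Grade 3 wording.* The bullet names recurrence after initial improvement and draws no distinction between spontaneous return and return on restart. Read literally, the sequence in step 1 meets it.
3. *Consequence of the grade.* Section 5.3 stops nivolumab permanently at Grade 3. Section 6.2 does so for a drug-related Grade 3 infusion reaction, whatever its duration. Section 6.2 does not itself mention recurrence; it applies only because the 5.3 wording makes the event Grade 3.
4. *Consequence under the Grade 2 steps.* Drug is withheld for the day, and the premedication sentence then covers later infusions for all Grade 2 reactions. The two sentences together leave the patient on the dosing schedule.

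**Infusions at stake.** Section 5.1 schedules doses on Days 1, 15 and 29, then "Cycle 4 = Day 43 if stable disease or response after day 29". A patient with stable disease or response has 4 scheduled doses; one who progresses has 3. After recurrence at dose k, the number remaining is 4 − k or 3 − k:

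| Recurrence at dose | Stable disease or response | Progression |
|---|---|---|
| 1 | 3 | 2 |
| 2 | 2 | 1 |
| 3 | 1 | 0 |

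Every entry becomes 0 if an aborted infusion counts as a missed dose under section 6.

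**How often.** Section 5.3 calls infusion reactions unlikely, and the documents give no recurrence rate. The rates r below are assumptions. With up to 19 patients enrolled (section 11.3), the expected number is 19r and the chance of at least one is 1 − (1 − r)^19:

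| Assumed r | Expected patients | Chance of at least one |
|---|---|---|
| 0.5% | 0.095 | 0.091 |
| 1% | 0.19 | 0.174 |
| 2% | 0.38 | 0.319 |

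**Effect on the safety stopping rule.** Section 11.4 counts Grade 3 and 4 events at least possibly related to nivolumab. Sections 5.3 and 8.6 require CTCAE grading. If the event is graded as the 5.3 wording implies, it is already in the count, so the change is 0.

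**The case against.** The strongest defence is that the two instructions can both be obeyed. Withholding drug for the rest of a visit does not order a dose at the next one. Staff can stop the infusion, grade the event 3 and discontinue under 6.2 without breaching any sentence. The premedication advice is only a recommendation and is most naturally meant for reactions that do not recur. This much stands: a reader might infer two commands that cannot both be followed, and the documents do not go that far. The problem comes from the recurrence sentence combined with an unqualified premedication sentence.

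It also stands that 6.2 is not a second, independent contradiction, because it depends on the Grade 3 wording in 5.3. One can further argue that the Grade 2 paragraph is the only text dealing with a deliberate restart and so governs that case. The literal Grade 3 wording favours the other reading, but the protocol never says which was meant. That is a reason to clarify it.

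Other defences help less. The clause in 5.3 allowing local modification of treatment advice does not say which grade applies and does not set 6.2 aside. The CTCAE requirement leads to the right answer only if someone regrades, and the Grade 2 steps do not prompt that. Section 6 would end dosing if an aborted infusion were a missed dose, but it leaves this unstated, and the Grade 2 paragraph plainly expects further doses.

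**Conclusion.** The concern holds as a gap in the dosing instructions. Followed as printed, the Grade 2 steps can lead to re-exposure of a patient whom the protocol's own Grade 3 wording takes off drug. The conclusion rests on reading recurrence after restart as recurrence after initial improvement, which is the literal sense.

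The size is small: 0 to 3 further infusions for an affected patient, and 0.1 to 0.4 expected patients among 19 at the assumed rates, with a 9% to 32% chance of at least one. A reader might infer that the efficacy result or the section 11.4 boundaries are compromised. The documents do not support this: the Simon design figures do not depend on the rule, and the safety count is unchanged under correct grading. The case for acting is that the hazard is avoidable and the correction cheap.

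**What to change.** In the Grade 2 paragraph of 5.3, replace the recurrence sentence and the sentence after it (intravenous diphenhydramine and bedside monitoring) with:

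*If symptoms recur after restart, the reaction is Grade 3: stop the infusion, follow the Grade 3 management below and permanently discontinue nivolumab (6.2); the subject proceeds to surgery.*

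Both sentences must go; otherwise the lighter Grade 2 treatment would directly follow an instruction to use Grade 3 management. Begin the Grade 2 premedication sentence with *For Grade 2 reactions that do not recur,*. If the sponsor instead means such a recurrence to stay Grade 2, the protocol should say so and amend the Grade 3 description to match.

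The cost is a short text change, with no new data or procedures. A rare patient stops dosing early. With fewer than two doses received, that patient is not evaluable for efficacy (11.1.2) and is replaced under 11.2.1, within the allowance of 19 − 17 = 2 patients in 11.3. Recurrence at dose 2 raises the question whether a partial infusion counts as a dose received, which 11.1.2 should answer. The event counts as Grade 3 towards the 11.4 boundary, which starts at 2 events in 3 to 9 patients. Correct grading under the present 5.3 wording already requires that, but it is worth stating.
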